## **VII. Treatment of Subjects:**

### ***A. Intended Use***

The BiPAP A40 EFL Ventilator (Vector ventilator) is intended to provide non-invasive ventilatory support to treat patients weighing over 10Kg (22lbs.) with Obstructive Sleep Apnea (OSA) or Respiratory Insufficiency. It is intended to be used within the home, institutional/hospital, and diagnostic laboratory environments. This device is not intended for life support. The BiPAP A40 EFL screening and therapy is intended for patients weighing over 30Kg (66lbs.) with obstructive sleep apnea (OSA) or Respiratory Insufficiency with primary cause being chronic obstructive pulmonary disease (COPD) to screen for the presence, and abolishment of Expiratory Flow Limitation

### ***B. Contraindications:***

- Inability to maintain a patent airway or adequately clear secretions
- At risk for aspiration of gastric contents
- Diagnosed with acute sinusitis or otitis media
- Epistaxis, causing pulmonary aspiration of blood
- Hypotension, defined as systolic BP < 90
- Existing respiratory failure

There will be no restrictions on concomitant medications during the course of the study. If medications change during the study, participants will be asked to let their pulmonologist know.

### ***C. Monitoring:***

This clinical study will be monitored by Philips (Sponsor) in compliance with the Code of Federal Regulations (CFR) for clinical research; namely, 21 CFR Parts 50, 54, 56 and 812 and others as applicable. The purpose of such monitoring is to assure that the study remains in compliance with the approved protocol, investigator agreement and regulatory requirements, to verify the completeness, reliability and accuracy of study data and to resolve any issues that arise during the conduction of the study. The Sponsor will conduct monitoring visits periodically as specified by the monitoring plan. Monitoring will be conducted by trained clinical research professionals.

It has been determined that this study does not require a Data Safety Monitoring Board (DSMB).

### ***D. Unscheduled Visits***

Unscheduled calls and or visits will be documented in the participant study file upon occurrence. Participants may be asked to receive additional phone calls and or visits in order to evaluate any device issues should they occur.

## **VIII. Assessment of Performance**

Device performance will be based on the following patient physiological and device recorded parameters:

- Daytime PaCO2 levels after 30-day period, method (Visits 3 and 4)
- Nocturnal TCO2 levels during sleep study (Visits 3 and 4)
- Nocturnal SpO2 levels during sleep study (Visits 3 and 4)
- Ventilator collected parameters over the 30-day use period (RR, MV, usage hours) (Visits 3 and 4)

## **IX. Assessment of Safety**

Serious adverse events, occurring during the course of the study will be collected, fully documented, and reported to the Western Institutional Review Board, according to their guidelines, by the Principal Investigator, [name], MD or sponsor staff. Serious adverse events will be reviewed by the Sponsor within 24 hours of the study team being aware of the event.

### **Adverse Events**

Adverse event means any untoward medical occurrence associated with the use of an intervention in humans, whether or not considered intervention-related.

An adverse device effect (ADE) is an AE related to the use of an investigational medical device.

## **Serious Adverse Events**

An AE or suspected adverse reaction is considered "serious" if, in the view of either the investigator or sponsor, it results in any of the following outcomes: death, a life-threatening AE, inpatient hospitalization or prolongation of existing hospitalization, a persistent or significant incapacity or substantial disruption of the ability to conduct normal life functions, or a congenital anomaly/birth defect. Important medical events that may not result in death, be life-threatening, or require hospitalization may be considered serious when, based upon appropriate medical judgment, they may jeopardize the participant and may require medical or surgical intervention to prevent one of the outcomes listed in this definition. Examples of such medical events include allergic bronchospasm requiring intensive treatment in an emergency room or at home, blood dyscrasias or convulsions that do not result in inpatient hospitalization, or the development of drug dependency or drug abuse.

## **Unanticipated Serious Adverse Device Effect**

A USADE is a serious ADE which by its nature, incidence, severity or outcome has not been identified in the current version of the risk analysis report.

## **Severity of Event**

The following guidelines will be used to describe AE severity:

- **Mild** – Events require minimal or no treatment and do not interfere with the participant's daily activities.
- **Moderate** – Events result in a low level of inconvenience or concern with the therapeutic measures. Moderate events may cause some interference with functioning.
- **Severe** – Events interrupt a participant's usual daily activity and may require systemic drug therapy or other treatment. Severe events are usually potentially life-threatening or incapacitating. Of note, the term "severe" does not necessarily equate to "serious".

## **Relationship to Study Intervention**

All AEs must have their relationship to study intervention assessed by the clinician who examines and evaluates the participant based on temporal relationship and his/her clinical judgement. The degree of certainty about causality will be graded using the categories below. In a clinical trial, the study product must always be suspect.

- **Related** – The AE is known to occur with the study intervention, there is a reasonable possibility that the study intervention caused the AE, or there is a temporal relationship between the study intervention and event. Reasonable

possibility means that there is evidence to suggest a causal relationship between the study intervention and the AE.

- **Not Related** – There is not a reasonable possibility that the administration of the study intervention caused the event, there is no temporal relationship between the study intervention and event onset, or an alternate etiology has been established.

### **Adverse Event Assessment and Follow-Up**

Adverse events will be collected on an ongoing basis following signing of informed consent. Detailed information regarding the event will be recorded on the appropriate form in the electronic case report form (eCRF), where the Investigator will determine the severity of the event, relationship to study product (assessed only by those with the training and authority to make a diagnosis), and time of resolution/stabilization of the event. Follow-up data to ascertain the existence of residual effects from the event will be obtained. Serious adverse events must be reported to the sponsor within 24 hours of discovering the occurrence of the SAE. The research staff is required to complete and submit the sponsor's standard SAE form detailing the event.

### **Serious Adverse Event and Unanticipated Adverse Device Effect Reporting**

The study investigator will complete an SAE/Unanticipated Adverse Device Effect Form and submit to the study sponsor and to the reviewing IRB as soon as possible, but in no event later than 5 working days after the investigator first learns of the effect. The study sponsor is responsible for conducting an evaluation of an unanticipated adverse device effect and shall report the results of such evaluation to local regulatory authorities and to all reviewing IRBs and participating investigators within 10 working days after the sponsor first receives notice of the effect. Thereafter, the sponsor shall submit such additional reports concerning the effect to local regulatory authorities.

### **Device Deficiencies**

All device deficiencies, use or user errors, and equipment failures will be documented. Use or User errors will be captured as part of the source documentation. Device deficiencies and equipment failures will be kept on a separate log. The serial numbers and type of deficiency/failure will be captured. Unanticipated device deficiencies that lead to SAE's will be reviewed with the principal investigator (PI) and reported to the IRB as required.

All unexpected adverse events will be collected and reviewed. As any events will be reported electronically or directly from a person the study team will collect the onset, duration, intensity and treatment required, outcome and action taken. In addition to

adverse event reporting, the study staff will report a summary of the protocol findings, participant recruitment, drop-outs, and events to the IRB annually.

All Adverse Events will be followed for 30 days or until resolution, whichever comes first.

## **X. Device Deficiencies**

All device deficiencies use or user errors, and equipment failures will be documented. Use or User errors will be captured as part of the source documentation. Device deficiencies and equipment failures will be kept on a separate log. The serial numbers and type of deficiency/failure will be captured. Unanticipated device deficiencies that lead to SAE's will be reviewed with the PI and reported to the IRB as required.

## **XI. Statistical Methods**

### **Determination of Sample Size**

No power analysis was performed to determine the sample size for this pilot study. The results of this study may be used to power a larger pivotal trial.

### **General Considerations**

The primary analysis will be performed including all consented participants. Descriptive data tables will be provided for all variables of interest. Continuous data will be presented by mean, standard deviation, median, minimum, and maximum observation. Data will be presented in the untransformed and transformed format (if applicable) for each continuous variable. Categorical data will be presented as frequencies and percentages. All formal statistical analyses will be performed using either SAS® or SPSS® software. Significance tests will be conducted at a two-sided significance level of  $p < 0.05$ .

There are no statistical criteria for terminating the study. No sensitivity analysis will be completed, and any deviations to the original statistical plan will be noted in the analysis report.

### **Participant Disposition**

Participant disposition, including the total number of participants enrolled, completed, early terminations and withdrawals, will be presented. A listing will be provided with the reasons for discontinuation.

### **Demographics and Baseline Characteristics**

Participant demographics (e.g., age and gender) and baseline characteristics will be summarized for all participants enrolled and for evaluable participants.

## **Primary Analysis**

Since this was a crossover study, the endpoints were compared between the two therapies as paired samples. For each continuous endpoint, the paired differences will be examined for normality using the Shapiro-Wilk and Kolmogorov-Smirnov tests, and if the distribution does not deviate significantly from normality, the treatment effect will be examined using a paired t-test; otherwise, the endpoint was examined using the non-parametric Wilcoxon Signed-Ranks test. Categorical data will be evaluated using the McNemar Test.

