### **Secondary Endpoints:**

1. Average 30-day Ventilator Usage hours
2. Patient Comfort and Therapy Preference based questionnaire responses

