### **Randomization:**

Participants will be randomly assigned to either 1) Vector NIV followed by SOC NIV or 2) SOC NIV followed by Vector NIV. Randomization will be generated via a randomization website. For the SOC NIV therapy, participants will be required to use a Vector Device in place of their current NIV device. The Vector therapy will not be enabled, and the device will be set according to their current SOC NIV prescription.

**Cohort 1 (NIV Current Users):** Participants in Cohort 1, regardless of randomized therapy order, will be required to undergo the Vector device titration at study visit 2. (Appendix A) For the participants randomized to SOC NIV first, the settings determined from the Vector device during the randomization visit will then be applied when they cross over to Vector NIV at visit 3.

**Cohort 2 (NIV Naïve):** Participants in Cohort 2, regardless of randomized therapy order, will be required to undergo the Vector device titration at study visit 2. (Appendix A) Participants in cohort 2 who were randomized to SOC NIV first will have previously been titrated to SOC NIV therapy at visit 1.

Initiation of the Vector NIV titration will take place under the supervision of the study investigator, research coordinator and / or healthcare professional (Respiratory Therapist, Sleep Technician, etc.). Appendix A outlines the protocol and device settings that will be used for the Vector device titration. For the participants in Cohort 2 that are initially randomized to SOC arm, clinical study staff will follow currently established NIV standard of care titration protocols. After successful completion of the Vector NIV titration, participants will be given one-on-one operational instructions on the device by clinical study staff. They will also be given a user manual, mask, and tubing and be asked to use the device at home for 4 to 6 weeks. For the participants in Cohort 2 that are randomized to SOC arm, they will continue to use the Vector device as they did during the 2-week home acclimation period with the previously determined SOC NIV settings.

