### **Phone Follow-ups:**

Participants will be sent home with the Vector device with their randomized therapy. During the initial week, the participant will be contacted daily to determine if there are any problems with the device and to encourage compliance. Participants will be asked to use the Vector device at night for the following 6 weeks. Participants will then be contacted weekly from week 2 to the last week of their take home period (maximum of 6 weeks). During the second take home period, all participants will be called daily during the first week only.

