### **Scoring**

All sleep studies will be scored by the qualified site personnel. All sleep variables will be classified and scored using the 2007 AASM criteria additionally, all sleep variables will be scored using a modified Hypopnea rule as defined below.

- Apneas will be scored according to AASM Scoring Manual rules VIII.3.A, B.
- Hypopneas will be scored according to the AASM Scoring Manual rule VIII.4.A for desaturations with a nadir below 90%.

For hypopneas yielding desaturations with a nadir of 90% or greater, a modified rule VIII.4.A will be used that requires an arousal (rule V.1.A) to accompany the event for scoring as a hypopnea.

**NOTE:** If the participant slept less than 3 hours on any lab night, they, may be asked to repeat the overnight sleep test. If the patient is unwilling to repeat the sleep test, furthermore, a replacement participant will then be enrolled.

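### The crossover is analysed as pooled pairs without a period term; if periods differ, the SD is inflated and, with unequal completed sequences, the estimate is biased

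*Combined protocol and SAP*

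**What the plan says.** Primary Analysis (section XI) states: "Since this was a crossover study, the endpoints were compared between the two therapies as paired samples". Continuous endpoints are tested by paired t-test if the differences pass normality checks and by Wilcoxon signed-rank otherwise. Categorical data go to McNemar. No period or sequence term appears there or elsewhere in the document. General Considerations adds: "No sensitivity analysis will be completed, and any deviations to the original statistical plan will be noted in the analysis report".

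Phone Follow-ups (section V) sets the contact schedule. In the first week at home "the participant will be contacted daily to determine if there are any problems with the device and to encourage compliance". After that, "Participants will then be contacted weekly from week 2 to the last week of their take home period". For period 2 the text is: "During the second take home period, all participants will be called daily during the first week only". The schedule table also lists a second week-4 diary reminder call after visit 3, and the section on actigraphy and the sleep diary says the team will telephone about the diary.

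The first secondary endpoint in section IV is "Average 30-day Ventilator Usage hours". Section V gives 1:1 allocation to the two orders. On method, Randomization says only "Randomization will be generated via a randomization website", with no mention of blocking. The aim is 30 completers in total, with no target per sequence.

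**The concern.** In a two-period crossover, a paired test on Vector minus SOC does not separate therapy from period. If outcomes shift between periods for any reason other than therapy, the shift enters the differences with opposite sign in the two sequences. With equal sequences it cancels from the mean but not from the SD. With unequal sequences part of it stays in the mean.

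The protocol supplies a possible source. Compliance calls continue weekly through period 1, but in period 2 routine calls are described for week 1 only, whichever therapy is in use. Usage hours are the endpoint most directly exposed; any route to PaCO2 is indirect.

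The estimate and its SD are what a pilot hands on. Determination of Sample Size says the results may be used to power a pivotal trial, and section XVII says the data may support regulatory clearance. As written, the analysis would neither remove a period effect nor report one.

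**Working it through.** **Inputs from the document.** 30 completers; 1:1 allocation; two-sided 5% level; paired analysis. The document gives no SD, effect size or period effect, and no power calculation to reproduce.

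**Assumptions.** Within-sequence SD of the differences = 1. Period effect P (period 2 minus period 1) = 0.25 or 0.5 SD. Power is for a true difference of 0.5 SD. Normal differences, no carryover.

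**Model.** Let d = Vector minus SOC, with true therapy effect τ. The mean of d is τ + P in the n1 participants who have SOC first and τ − P in the n2 who have Vector first. With N = n1 + n2:

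- Bias of the pooled mean = P(n1 − n2)/N.
- Expected pooled variance = 1 + 4P²n1n2/[N(N − 1)].
- SE of the period-adjusted estimate (mean of the two sequence means) = ½√(1/n1 + 1/n2), on N − 2 degrees of freedom, whatever P is.

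**SD at 15:15.** 4 × 225/(30 × 29) = 1.0345.
- P = 0.25: √(1 + 0.0625 × 1.0345) = 1.032.
- P = 0.5: √(1 + 0.25 × 1.0345) = 1.122.

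**Bias.**
- 18:12: P × 6/30 = 0.05 or 0.10 SD.
- 20:10: P × 10/30 = 0.08 or 0.17 SD.

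**Error rates of the paired t-test** (simulation, 100,000 trials per cell):

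| Split | P | Bias (SD) | Type I error | Power, bias opposing / favouring the effect | Adjusted power |
|---|---|---|---|---|---|
| 15:15 | 0.25 | 0 | 4.3% | 73% (no bias) | 75% |
| 15:15 | 0.5 | 0 | 2.9% | 67% (no bias) | 75% |
| 18:12 | 0.25 | 0.05 | 5.1% | 64% / 81% | 74% |
| 18:12 | 0.5 | 0.10 | 5.3% | 47% / 84% | 74% |
| 20:10 | 0.25 | 0.08 | 6.5% | 57.5% / 86% | 70% |
| 20:10 | 0.5 | 0.17 | 10% | 34% / 91% | 70% |

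The adjusted analysis has no bias and type I error of 4.9% to 5.2% throughout.

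**Chance of such splits.** If allocation is simple (assumed), the larger sequence follows from Binomial(30, 0.5): 18:12 or worse has probability 36%, 20:10 or worse 10%, and exactly 15:15 14%.

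**Averaged over those splits.** Type I error of the paired test is about 5.0%. Power, pooled against adjusted, is:
- P = 0: 75% v 74%
- P = 0.2: 73.8% v 73.8%
- P = 0.25: 73.0% v 73.9%
- P = 0.5: 65.9% v 73.9%

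**Usage hours.** With an assumed SD of 1 to 2 h, P = 0.5 SD means that nightly use shifts by 30 to 60 minutes between periods. The bias is then 0.2 × (30 to 60) = 6 to 12 minutes per night at 18:12, and (30 to 60)/3 = 10 to 20 minutes at 20:10.

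**The case against.** The strongest reply is that the planned test is not invalid. It is unbiased with equal sequences, and its type I error averages 5% over simple randomisation. With no period effect it is slightly more powerful on average than the adjusted test, and at P = 0.25 it loses only about 1 point. The pooled interval is no wider than the adjusted one below P of about 0.05 SD at 15:15, 0.21 at 18:12 and 0.37 at 20:10. All of this stands. It limits the size of the point, but does not help a trial that happens to draw an uneven split.

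The evidence for a period effect is also modest. A reader might infer that contact stops after week 1 of period 2. The document does not support that, because a week-4 diary reminder call is scheduled; what falls away is the routine weekly calls. Both cohorts must also show about 4 hours of nightly use before randomisation, which limits early-learning effects, though it does not equalise contact between periods.

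A reader might also take the estimate of 50 enrolled for 30 completers as a sign of unequal sequences. It is not: it includes losses before randomisation, from failed EFL or EPAP screening and failed acclimation. The Scoring note that "a replacement participant will then be enrolled" after an unusable lab night does not name the sequence the replacement joins, but it covers only participants who sleep under 3 hours and decline a repeat.

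Finally, this is an unpowered pilot. The 95% interval for an SD from 30 pairs runs from about 20% below to 34% above the estimate, wider than the 3% to 12% inflation at issue. Power for a 0.5 SD difference is also only a yardstick, since the hypothesis for PaCO2 is of equal levels. Both remarks are fair. But the inflation is systematic, and a needlessly wide interval makes a non-significant PaCO2 difference easier to mistake for equality.

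**Conclusion.** The point holds as a cheap improvement. The omission is certain: there is no period term, and no sensitivity analysis that would reveal a period effect. The harm is conditional on an assumed period effect and, for bias, on the split of completers. At P = 0.25 SD the average cost is about 1 power point. At P = 0.5 SD it is about 8 points, and an uneven split can bias the estimate by 0.10 SD (18:12) or 0.17 SD (20:10).

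Two stronger conclusions are not supported. The document does not show that a period effect exists. Nor does it show that the paired test has an inflated type I error in general: inflation appears at splits such as 20:10, and at 15:15 the test is conservative. The 36% and 10% probabilities rest on simple randomisation, which the document neither states nor excludes.

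**What to change.** In Primary Analysis, make the analysis of continuous endpoints period-adjusted: a linear mixed model with therapy, period and sequence as fixed effects and participant as a random effect. For complete pairs this equals the Hills-Armitage comparison. As the non-parametric form, replace the signed-rank test by the rank-sum test on period differences between sequences. Report the number of completers by sequence, the estimated period effect, and the period-adjusted SD for any pivotal planning.

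The cost is a change of SAP wording and a few lines of code. At 15:15 it takes one degree of freedom (29 to 28) and less than 1 power point. If there is no period effect, the SE relative to 1/√30 = 0.1826 is:
- 18:12: ½√(1/18 + 1/12) = 0.1863, or 2% larger.
- 20:10: ½√(1/20 + 1/10) = 0.1936, or 6% larger, with power falling from 75% to 70%.

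Averaged over simple randomisation, the loss when there is no period effect is about 1.6 points. Like the planned test, the adjusted analysis assumes no carryover and does not address it.
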